2.2 STUDY OBJECTIVES

Objectives of this pilot project include:

1. Construct a concurrent external control arm for recifercept phase 2 clincial trial using achondroplasia patients from a prospective observal natural history study 2. If objective #1 is met, the following will be compared to examine differences between patients enrolled in the recifercept phase 2 clincial trial and those in the concurrent external control:

- Selected anthropometric measurements, including but not limited to: standing height, sitting height, knee height, arm span, length of the legs, sitting height/standing height ratio, arm span to height/length difference, knee height/lower segment ratio
- Achondroplasia-related orthopaedic complications (including lordosis, kyphosis, small foramen magnum, spinal stenosis), and other achondroplasiarelated complications (including apnea, AOM, and hydrocephalus)
- Differences in functional status and health-related quality of life

PFIZER CONFIDENTIAL

CT24-WI-GL03-RF03 2.0 Non-Interventional Statistical Analysis Plan For Secondary Data Collection Study 01-Jun-2020 Page 8 of 17

3 HYPOTHESES AND DECISION RULES

3.1 STATISTICAL HYPOTHESES

This study includes an CCL element and specific hypotheses to be tested. That null hypothesis is limited to a comparison of height Z-Score. The null hypothesis for that objective is as follows:

Null: Mean Change from Baseline of Height Z-Score up to 12 months is no different between patients on treatment and patients in the natural history study.

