9.3. Variables

Table 3. Listing of all variables of importance

Variable	Role	Phase II Recifercept Clinical Trial (C4181005)	Natural History Study (C4181001)	Operational definition
Achondroplasia treatment	Exposure	Recifercept dosage and duration: Recifercept dosage: 1mg/kg once-weekly 2mg/kg twice-weekly 1.5mg/kg once-daily	Achondroplasia-related treatment and duration Collected every 3 months	
Height Growth	Primary outcome	Collected every 3 months until end of study participation	Collected every 3 months until end of study participation	Defined as increase in height growth above expected growth in reference population, defined as the height growth in the achondroplasia reference population +50%
Anthropometric Measurements	Secondary outcome	 Standing height Sitting height Knee height Arm span Length of the legs Sitting height/standing height ratio Arm span to height/length difference knee height: lower segment ratio Collected at 1m, 3m, 6m, 9m, 1y 	 Standing height Sitting height Knee height Arm span Length of the legs Sitting height/standing height ratio Arm span to height/length difference knee height: lower segment ratio -collected at baseline, every 3m, and end of study visit 	Length of the legs will be calculated as the difference between standing and sitting height
Achondroplasia- related orthopaedic complications	Secondary outcome	Baseline collection - foramen magnum decompression - cranial surgery Occurrence during follow-ups	 Lordosis Kyphoscoliosis Small foramen magnum Spinal stenosis collected at 6m, 1y, 2y, 3y, and 4y Collected every 3 months until end of study participation 	

PFIZER CONFIDENTIAL CT24-WI-GL02-RF02 3.0 Non-Interventional Study Protocol Template For Secondary Data Collection Study 23-May-2022 Page 19 of 26

Other achondroplasia- related complications	Secondary outcome	 Sleep disordered breathing Acute Otitis Media (AOM) Hydrocephalus 	 Sleep disordered breathing Acute Otitis Media (AOM) Hydrocephalus 	
CCI				
Demographics	Covariate	- Age	- Age	
		- Gender - Race and ethnicity	- Gender - Race and ethnicity	
		Collected at baseline	Collected at baseline	
Puberty	Covariate	Tanner stage	Tanner stage	
		Collected at baseline	Collected at baseline	
Weight	Covariate	Body weight	Body weight	
		Collected every 3 months until end of	Collected every 3 months until end of	
		study participation	study participation	
History of	Covariate	Sleep-disordered breathing	Sleep-disordered breathing	

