2 INTRODUCTION

- Note: in this document, any text taken directly from the non-interventional (NI) study protocol is *italicised*.
- Achondroplasia is a heritable autosomal dominant disorder and is the most common form of skeletal dysplasia in humans, with a global birth prevalence of 1 in 25-30,000 or ~250,000 individuals worldwide (1–3). Achondroplasia is caused by a single-point gain-of-function mutation in the gene encoding the fibroblast growth factor receptor 3 (FGFR3) (2,4). FGFR is a key inhibitory regulator of endochondrial ossification and its over-activiation interferes with normal chondrocyte maturation and causes shorter long bones and changes in flat bones such as the occipital bone and vertebrae.

- Achondroplasia results in short stature and a range of severe complications due to abnormal ossification centers in the cranial base, facial bones, vertebrae, rib cage, and joints. Lordosis, kyphosis, small foramen magnum, and spinal stenosis are the most common achondroplasia-related orthopaedic complications. Other achondroplasia related complications include sleep-disordered breathing, otitis media, and hydrocephalus. Medical complications associated with achondroplasia greatly impact physical and psychosocial functioning, self-esteem, and patient quality of life (3,5).
- Currently, vosoritide is the only treatment approved by EMA (for achondroplasia patients aged 2 years and older with open growth plates) and FDA (for achondroplasia patients aged 5 years and older with open growth plates) to increase linear growth. It is an analog of C-type natriuretic peptide and works by binding to a receptor called natriuretic peptide receptor type B (NPR-B), which reduces the activity of FGFR3. Other available treatments are either aimed at limb lengthening with surgery or are interventions to treat the complications associated with achondroplasia. Recifercept is a modified soluble recombinant human FSFR3 under development for the treatment of achondroplasia. Recifercept is designed to be a decoy protein, competing for ligands of the FGFR3-G380R receptor responsible for achondroplasia and by forming inactive heterodimers with FGFR3 monomers. By binding free FGFR3-activating ligands and forming inactive dimers, recifercept reduces activation of the receptor, allowing chondrocyte proliferation and differentiation to proceed.

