2.1 STUDY DESIGN

• This is a retrospective cohort study using existing data from two ongoing studies: C4181001 and C4181005. The study population will include two independent study

PFIZER CONFIDENTIAL

CT24-WI-GL03-RF03 2.0 Non-Interventional Statistical Analysis Plan For Secondary Data Collection Study 01-Jun-2020 Page 5 of 17 cohorts: a) patients from Study C4181005 who have completed Visits 1 through 11 (at D183); b) patients from Study C4181001 who meet the eligibility criteria for Study C4181005 and have at least 6 months follow-up data. Eligible patients from Study C4181001 will be included as potential external controls for patients in Study C4181005, using propensity score methodology.

This pilot study has the potential to demonstrate the feasibility of Study C4181001 as concurrent external controls and provide viable study design options for the recifercept pivotal trial. It will also provide information on the efficacy of recifercept compared to clinical practices in the real world. Having an external control arm in the trial allows for increased efficiency and decreased product development time.

Study population

This retrospective cohort study will include achondroplasia patients from Study C4181005 and those from Study C4181001 who meet the inclusion and exclusion criteria of Study C4181005. Study C4181005 is a single-arm trial to evaluate the safety and tolerability of recifercept doses and dosing regimen, and efficacy to increase height growth in achondroplasia patients. Study C4181005 will include approximately 63 children with achondroplasia aged 3 months to 10 years (inclusive) with Tanner Stage 1. who are enrolled and randomized to receive one of three doses of recifercept (1mg/kg once-weekly, 2mg/kg twice-weekly, or 1.5mg/kg once-daily) subcutaneously for 12 months. Demographics, medical history, anthropometric measurements, and patientreported outcomes in functional status and quality of life are collected approximately every 3 months. Study C4181001 is a prospective natural history study to collect the longitudinal anthropometric and disease-related complication data in children with achondroplais. It will include approximately 300 achondroplasia patients aged 0-15 years with Tanner Stage I recruited from global sites. Patient data will be collected at baseline and at every 3-month interval visits, for a maximum of 5 years. Further details on data sources are presented in Table 1.

Data source

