•	Primary objective	•	- Evaluate the safety and tolerability of recifercept doses and dosing regimens in participants aged ≥ 2 to <11 years with achondroplasia	•	- Collection of longitudinal anthropometric and disease- related complication data in children with achondroplasia
		•	- Assess efficacy of recifercept to increase height growth in children with achondroplasia		
•	Secondary outcomes	•	- To evaluate the pharmacokinetics of recifercept in participants aged ≥ 2 to <11 years with achondroplasia	•	- Investigation of potential serum biomarkers in children with achondroplasia
		•	- To assess efficacy of recifercept to improve ahondroplasia-related complications		

PFIZER CONFIDENTIAL

CT24-WI-GL03-RF03 2.0 Non-Interventional Statistical Analysis Plan For Secondary Data Collection Study 01-Jun-2020 Page 7 of 17

Treatment/cohort labels

Treatment are determined which protocol each participant is in and will be reported as such.

Protocol	Treatment	Label
C4181001	Not treated	
C4181005	Treated	Recifercept

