4 ANALYSIS SETS/POPULATIONS

4.1 FULL ANALYSIS SET

The Full Analysis set includes all patients who met the inclusion & exclusion criteria listed below.

Inclusion criteria

All patients from Study C4181005 who have completed Visits 1 through 11 (at D183) will be included in this project.

To construct a concurrent external control from Study C4181001, patients from Study C4181001 will need to meet the following eligibility criteria from Study C4181005:

- Documented, confirmed genetic diagnosis of achondroplasia from historical medical records (test must have been performed at a laboratory fully accredited for genetic testing under local regulations)
- Aged \geq 3 months to <11 years (up to the day before 11th birthday inclusive) at time of enrollment into Study C4181001
- *Have completed at least 2 valid height/length measurements (at least 3 months apart)*
- Assessed for Tanner stage 1 during physical examination before or at enrollment into Study C4181001 (must include assessment of breast development for females, or testicular stage for males)
- Able to stand independently for height measurements (if ≥ 2 years of age at enrollment); If aged < 2 years at enrollment, has a documented historical MRI brain/cervical spine performed in the previous 12 months.

PFIZER CONFIDENTIAL

CT24-WI-GL03-RF03 2.0 Non-Interventional Statistical Analysis Plan For Secondary Data Collection Study 01-Jun-2020 Page 9 of 17 • *Have at least 6 months of available follow-up data after enrollment into Study C4181001*

Exclusion criteria

- Presence of severe obesity (BMI > 95% percentile on Hoover-Fong BMI charts)
- Body weight <7kg or >30kg
- *History of chronic kidney disease (CKD) or renal impairment*
- History of receipt of any treatment that are known to potentially affect growth (including oral steroids > 5 days in the last 6 months before enrollment, high dose inhaled corticosteroids (>800 mcg/day beclametasone equivalent) and medication for attention deficient hyperactivity disorder)
- Less than 6 months since fracture or surgical procedure of any bone determined from the baseline visit date.
- Presence of any internal guided growth plates/devices
- *History of removal of internal guided growth plates/devices within 6 months prior to enrolment*

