5 ENDPOINTS AND COVARIATES

For the untreated group, baseline value is defined as the value recorded at the date of informed consent, whereas for the treated group the baseline value is the value taken at Day 1.

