Another method to construct an external control for C4181005 for the purpose of estimating the Average Treatment Effect (ATE) of recifercept is Inverse Probability Weights (IPW). IPW will use PS to weight the observations prior to the analysis of height growth. Weights are calculated for each subject as 1/PS for Recifercept and 1/(1-PS) for the untreated group. Standardized differences between the untreated and Recifercept groups will be assessed both before and after weighting. Standardized mean differences of <10% may be considered a negligible difference.

7.2.2 Objective 2

Achondroplasia disease measures including height growth, anthropometric measurements, difference in functional status and health-related of life will be summarized using descriptive statistics.

Analyses of Height Z-Score and Arm-Span-to-Height Difference

If objective 1 is met, either a matched dataset – exclusively with a ratio of treated to untreated of 1:1 - via PS or a dataset augmented by IPW will be used to analyze height Z-Score. Baseline summaries of Height Z-score and Arm-Span to Height-difference and change from baseline a months 3, 6, 9, and 12 will be presented.

7.2.3 Safety Analyses

Not applicable.

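### C4181001 controls are analysed as untreated by protocol number, with no rule for a control who starts vosoritide or another growth-affecting treatment during the 12 months

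*SAP*

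**What the plan says.** Treatment group follows study membership. SAP 2.1 states: "Treatment are determined which protocol each participant is in and will be reported as such". The table beneath it gives C4181001 the label *Not treated*. SAP 5 keeps that usage ("For the untreated group, baseline value is defined as the value recorded at the date of informed consent"), as does the weighting rule in 7.2.1 ("1/(1-PS) for the untreated group"). SAP Section 1, item 1, explains the change of endpoint by saying that this study has an arm regarded as placebo.

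SAP 2.1 also says the project will inform on the "efficacy of recifercept compared to clinical practices in the real world", which is a different comparator.

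The hypothesis in SAP 3.1 runs over follow-up: "Height Z-Score up to 12 months is no different between patients on treatment and patients in the natural history study".

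The only rule on growth-affecting treatment is an exclusion in SAP 4.1: "History of receipt of any treatment that are known to potentially affect growth". Its oral-steroid example is dated to the 6 months before enrolment. The fracture or surgery and device-removal exclusions are dated to baseline or enrolment.

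SAP 2 notes that "vosoritide is the only treatment approved by EMA" from age 2 and by the FDA from age 5, to increase linear growth. Controls may be aged 3 months to under 11 years. Protocol 9.3, Table 3, lists for C4181001, with the role of exposure: "Achondroplasia-related treatment and duration Collected every 3 months". The SAP makes no use of that field.

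**The concern.** An untreated comparator and a real-world-care comparator agree only while no control receives a growth treatment. Once one does, they need different handling. Heights after the start do not belong in an untreated comparison, but they do belong in a comparison with clinical practice. The SAP uses both descriptions and has no rule for the case where they part. Followed as written, the plan keeps those heights under the label *Not treated*.

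What is at stake is the meaning of the objective 2 result. A reader would take it as recifercept against no treatment without being able to tell whether that is so. How far C4181001 children stay untreated over a year is also worth knowing for the project's stated purpose, which is to judge that study as a control source for a pivotal trial.

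**Working it through.** **Step 1. Is there a rule after entry?**

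| Place | What it does about a control starting treatment after baseline |
|---|---|
| SAP 4.1 | Eligibility only. At least 6 months of follow-up is required, with no condition that it be untreated |
| SAP 5.4 | Covariates: not applicable |
| SAP 6 | No imputation. Nothing on leaving heights out |
| SAP 7.2 and 7.2.2 | Treatment, visit, their interaction, age and gender. No time-varying treatment and no stopping rule |
| SAP 10.3 | Propensity model uses sex, age and white race. Outcome models use drug and month. No filter is described as treatment-related |

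No rule is found.

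**Step 2. What could it do to a Month 12 contrast?** The plan gives no figure on this point. Protocol Table 1 sizes the height-growth ratio that the amended SAP dropped.

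Inputs from the documents:
- two-sided alpha of 0.05 (SAP 3.2)
- visits at Months 3, 6, 9 and 12 (SAP 7.2.2)
- 63 trial children (SAP 2.1)
- about 30 pairs at the first data release (Protocol 9.6)

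Inputs assumed:
- q, the share of controls who start
- m, the month of starting
- v, the yearly Z-score gain from that treatment, 0.1 to 0.4
- SD of 12-month change, 0.3

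With visit categorical and a treatment-by-visit interaction (SAP 7.2 text), the shift against recifercept is q × v × (12 − m)/12.
- m = 3: 0.0375v, 0.075v and 0.15v for q = 5%, 10% and 20%.
- m = 6: 0.025v, 0.05v and 0.10v.

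The standard error is 0.3 × √(2/n): 0.0535 for n = 63 and 0.0775 for n = 30. Let s be the shift divided by the standard error. If recifercept has no effect, the two-sided error is Φ(−1.96 + s) + Φ(−1.96 − s). For m = 3:

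| q | v | Shift (Z) | s, 63 pairs | Error, 63 pairs | s, 30 pairs | Error, 30 pairs |
|---|---|---|---|---|---|---|
| 10% | 0.1 | 0.0075 | 0.14 | 5.2% | 0.10 | 5.1% |
| 10% | 0.4 | 0.030 | 0.56 | 8.7% | 0.39 | 6.7% |
| 20% | 0.1 | 0.015 | 0.28 | 5.9% | 0.19 | 5.4% |
| 20% | 0.4 | 0.060 | 1.12 | 20.2% | 0.77 | 12.1% |

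**Step 3. What about the coded model?** SAP 10.3 fits a single drug term with linear month and random slopes. With balanced arms, that term weights the visits in proportion to (I + r²tt′)⁻¹1. Here t = (0.25, 0.5, 0.75, 1) and r is the random-slope SD over 12 months divided by the residual SD; the random intercept drops out. For q = 10% and m = 3 the control profile is 0.10 × v × (0, 0.25, 0.5, 0.75). The shift against recifercept is 0.0375v at r = 0, 0.0226v at r = 1, 0.0028v at r = 2 and −0.0086v at r = 3. The sign changes at r = 2.19 (r = 1.55 for m = 6).

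**Step 4. What does leaving out later heights cost?** If starters contribute nothing at Month 12, the standard error grows by √[(1 + 1/(1 − q))/2] = 1.013, 1.027 and 1.061 for q = 5%, 10% and 20%. Of 63 controls, 63 × (1 − q) = 59.9, 56.7 and 50.4 remain.

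**Step 5. Does leaving them out work?** This was simulated with 400,000 controls, slope SD 0.25 per year, residual SD 0.1, v = 0.25, m = 3 and a true Month 12 mean of 0.
- Keeping all heights gave about 0.009, 0.019 and 0.038 for the three values of q, in line with Step 2.
- Leaving out heights after the start brought the mean within 0.001 of 0, both when starting was random and when it depended on Month 3 growth.

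The check used an unstructured repeated-measures model. It does not test the coded random-slope model, the weighted analysis, or starting that depends on unmeasured growth.

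**The case against.** The strongest reply is that this may be a gap on paper only. The C4181001 protocol is not among the documents and may withdraw children who start vosoritide. The main clause of the growth-treatment exclusion carries no date, so in a retrospective selection it could be applied to the whole record. The null in SAP 3.1 names natural history patients, not untreated ones, so *Not treated* might mean only that recifercept was not given.

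The first two replies stand as possibilities, and a count of zero would settle the matter. Neither is stated, though. The undated clause is worded as a history and sits among entry criteria. Applied to later records, it would select controls on events after baseline, which would itself need saying. The third fits the null and the clinical-practice sentence, but not the placebo description in Section 1. If it is what is meant, the label should say so.

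The objection also limits the size. Every value of q, v, SD and m is assumed. Using 63 pairs takes every trial child as matched, whereas completion to Day 183, trimming and the caliper can only reduce that number. The 20.2% error is the corner of an assumed grid.

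Three stronger inferences are tempting, and the documents do not support them:
- *Controls were in fact treated.* Nothing shows this.
- *The result is biased against recifercept.* For a growth-promoting treatment that follows for a Month 12 contrast, but not for the coded drug term, whose sign depends on r.
- *Objective 1 fails.* Its test in SAP 7.2.1 is standardized mean differences below 0.1 on the matched variables, which later treatment cannot change.

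**Conclusion.** The point holds as a gap in the analysis rule, and closing it is an inexpensive improvement. The plan fixes the untreated label by study, regards the arm as placebo, and would count heights after a control's start of growth treatment as untreated.

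The effect is zero if no control started. Otherwise, for the Month 12 contrast, it is 2.5% to 15% of the other treatment's yearly Z-score gain for 5% to 20% starters at Month 3 or 6. That range rests wholly on assumed uptake and timing. No direction is claimed for the coded drug term. Which comparison should be the main one is an estimand choice that remains open; reporting the count and both runs does not depend on it.

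**What to change.** Add to SAP 7.2:

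1. From the C4181001 treatment field in Protocol Table 3, report how many matched or weighted controls had started a growth-affecting treatment other than recifercept (vosoritide, limb lengthening, a guided growth device or similar) by Months 3, 6, 9 and 12.
2. If the count is zero, report only the count.
3. If any control started, run the height Z-score model twice. The first run keeps all heights and is labelled as the clinical-practice comparison of SAP 2.1. The second leaves out control heights after the start and is labelled as the untreated comparison. Do not describe the all-heights result as being against *Not treated*.
4. Apply the same rule to C4181005 only for treatments other than recifercept, and only if that trial's data record them. For C4181005 the Table 3 treatment row lists only recifercept dosage and duration.
5. State that the second run assumes a starter's later untreated growth can be predicted from earlier heights.

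The cost is one count table, at most one extra model run, and a Month 12 standard error larger by about 1% to 6% in the second run for 5% to 20% starters. Bias remains in that run if starting depends on growth that was not measured.

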3.2 STATISTICAL DECISION RULES

The alpha level will be 0.05, 2-sided. No adjustments for multiple comparisons will be made.

4 ANALYSIS SETS/POPULATIONS

4.1 FULL ANALYSIS SET

The Full Analysis set includes all patients who met the inclusion & exclusion criteria listed below.

Inclusion criteria

All patients from Study C4181005 who have completed Visits 1 through 11 (at D183) will be included in this project.

To construct a concurrent external control from Study C4181001, patients from Study C4181001 will need to meet the following eligibility criteria from Study C4181005:

- Documented, confirmed genetic diagnosis of achondroplasia from historical medical records (test must have been performed at a laboratory fully accredited for genetic testing under local regulations)
- Aged \geq 3 months to <11 years (up to the day before 11th birthday inclusive) at time of enrollment into Study C4181001
- *Have completed at least 2 valid height/length measurements (at least 3 months apart)*
- Assessed for Tanner stage 1 during physical examination before or at enrollment into Study C4181001 (must include assessment of breast development for females, or testicular stage for males)
- Able to stand independently for height measurements (if ≥ 2 years of age at enrollment); If aged < 2 years at enrollment, has a documented historical MRI brain/cervical spine performed in the previous 12 months.

PFIZER CONFIDENTIAL

CT24-WI-GL03-RF03 2.0 Non-Interventional Statistical Analysis Plan For Secondary Data Collection Study 01-Jun-2020 Page 9 of 17 • *Have at least 6 months of available follow-up data after enrollment into Study C4181001*

Exclusion criteria

- Presence of severe obesity (BMI > 95% percentile on Hoover-Fong BMI charts)
- Body weight <7kg or >30kg
- *History of chronic kidney disease (CKD) or renal impairment*
- History of receipt of any treatment that are known to potentially affect growth (including oral steroids > 5 days in the last 6 months before enrollment, high dose inhaled corticosteroids (>800 mcg/day beclametasone equivalent) and medication for attention deficient hyperactivity disorder)
- Less than 6 months since fracture or surgical procedure of any bone determined from the baseline visit date.
- Presence of any internal guided growth plates/devices
- *History of removal of internal guided growth plates/devices within 6 months prior to enrolment*

